### 7.2 Datavant Death Data

We will link data from Arcadia to death data from Datavant, a private U.S. data curator, specializing in organizing health data. Datavant's mortality database contains information on deceased individuals in the U.S. and Canada. Datavant's Death Index contains information on individual deaths including year and month of death, gender, and cause of death, where available. Information is obtained from the Social Security Administration's Death Master File in addition to private obituaries, newspapers and claims data, and is updated on a weekly basis. In 2018, information was present for just over 2.4 million deaths.

In order to de-identify records, names, addresses, and social security numbers are removed in addition to modifications such as changing a person's date of birth to year of birth alone. Datavant's proprietary technology adds encrypted tokens to each record, constructed from the underlying personally identifiable information. Since these tokens correspond to unique individuals, they can be used to link death information to other health-related datasets.

## 8 STUDY SIZE AND STATISTICAL POWER

[figure not shown]
### 8.1 Study Size

According to the most recent available data from Arcadia (delivered to Exponent November 2022), ~37,000 patients had an apparent initiation of NB. Of those patients ~64% had linked, adjudicated claims data at some point in time. Seventy percent of apparent initiators were women.

### 8.2 Ranges of Statistical Power for MACE

In a similar population of overweight/obese individuals, Ritchey et al. found that the incidence rate of MACE was estimated at 2/1,000 person-years among individuals unexposed to weight loss drugs (95% confidence interval [CI], 1.85–2.17). Guided by this estimated incidence rate of MACE, **Figure 3** describes a range of plausible estimates for the statistical power of the NB safety study.

**Figure 3. Range of power estimates for the endpoint of MACE in the NB safety study**

This Figure was generated using a general cohort power calculation methodology.  
Abbreviation: NB, Naltrexone and Bupropion; PY, person-years; RR, relative risk

Assuming an incidence rate of MACE of 2 per 1,000 years of follow-up within this study, and that there are ~37,000 initiators of NB, it appears that we have greater than 80% power to detect a relative risk of 2.0.

## 9 DATA MANAGEMENT

### 9.1 Descriptive Statistics

Descriptive statistics will be used to summarize each covariate by treatment group for all study objectives. For dichotomous variables, we will report the number and proportion of patients with each covariate. For categorical variables, we will report the number and proportion of patients in each level of the covariate. For continuous variables, the mean and standard deviation will be estimated. Standardized differences in means and proportions will be used to assess covariate balance between weighted treatment groups.

## 9.2 Missing Data

Some biometric variables within the EHR (e.g., laboratory values, such as HbA1c) are expected to be missing in a non-random way. We will employ multiple imputation methods to address missing covariate data at baseline by creating standard intervals (e.g., within periods of one, three or six months) for ascertainment of important missing values. If multiple results are available in an interval, we will select the valid observation that is most proximal to the cohort entry date.

Consistent with our previous research on missing data within EHRs, we will then use multiple imputation methods to impute missing values within intervals with no observed values for a given patient. To account for the uncertainty of imputed values, we will produce 10 complete datasets to quantify within- and between-dataset variance and to correct standard errors. That is, the full analysis will be conducted within each of the 10 complete datasets, the results will be averaged across the datasets, and the measures of statistical uncertainty (e.g., CIs) corrected for the imputation. Because of the number of possible covariates requiring imputation, we will use a fully conditional specification of the multiple imputation procedure (i.e., chained equations), which does not require the stringent assumption that some models make about the joint distribution of missing covariates.

The multiple imputation procedure reduces the potential for missing data bias at the population level and relaxes the assumptions necessary to interpret results as unbiased estimates. [name] designed and successfully conducted a cohort study with a large EHR using these techniques, and the results of that study were similar to trial results of the same comparisons.

## 9.3 Crude Incidence Rate Difference (IRD) and Incidence Rate Ratio (IRR) Estimates

The incidence rate for each group is the cumulative number of observed endpoint events, divided by the total person-years of follow-up. The crude IRD is the absolute difference in the observed incidence rate between initiators of NB and initiators of lorcaserin, with no adjustment for differences in patient characteristics between groups. The crude IRR is the relative difference (i.e., ratio) in the observed incidence rate of initiators of NB, divided by the observed incidence rate for initiators of lorcaserin, with no adjustment for differences in patient characteristics between groups.

## 9.4 PS Matching Weights

PS matching weights will be used to control for confounding between treatment groups. A logistic regression model will be used to estimate the predicted probability of treatment with NB versus treatment with lorcaserin, conditional on pre-specified covariates. Each patient's PS, or predicted probability from the model, will be the probability that the patient received NB. The complement of each patient's PS (i.e., 1-PS) will be the probability that the patient received lorcaserin. Each patient will be assigned a matching weight, which is a function of their PS and the treatment received. The numerator of the matching weight is the smaller of the PS or the complement of the PS (1-PS). The denominator is the PS if the patient received NB, and it is 1-PS if the patient received lorcaserin. For example, a patient with a PS value of 0.6 (1-PS = 0.4) who received NB would have a matching weight of 0.4/0.6 or 0.667. These weights will be used in regression models to account for confounding.

Similar methods will be used to generate propensity score weights within the CAMELLIA-TIMI 61 comparability cohort. Covariates will include demographics, calendar time of treatment initiation, comorbidities, medications, cardiovascular procedures, and indicators of health care utilization as proxy for overall disease state, care intensity, and surveillance.

Matching weights are the weighting analog of 1:1 PS matching, but include the entire eligible patient population, are more statistically efficient than matching, and produce better balance on covariates. Thus, matching weights standardize the distribution of patient characteristics to the area of common support (or empirical equipoise) in which patients could have reasonably received either treatment.

## 9.5 Estimation of Adjusted IRD and IRR Estimates

This study will include analogs of intention-to-treat (ITT) and per-protocol analyses, in accordance with clinical trial conventions. Both analyses estimate the effect of NB on the incidence of MACE relative to comparators, but differ in the handling of person-time, as described below. We adopt the term ITT and refer to the per-protocol analogue as the *as-treated* analysis.

### 9.5.1 Intention-to-Treat Analysis

The ITT defines each day of follow-up for everyone according to their exposure status at the time of cohort entry (e.g., initiation of NB). Classification of person-time in the ITT analysis is subject to exposure misclassification as individuals discontinue treatment or switch to the other study drug before their end of follow-up. In contrast, the ITT estimate preserves the balance in

baseline covariates that will be achieved through PS matching weights because individuals remain in the cohort to which they were assigned at baseline, when the PS weights are applied. The results from this approach are best interpreted as providing an estimate of the effect of starting treatment – or intending to start treatment – on the rate of the outcomes.

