	
Inclusion and exclusion criteria for the main objective will ensure that only new users are included, and that the NB and comparison groups are comparable on risk factors for MACE after application of propensity score (PS) matching weights.
 
Inclusion and exclusion criteria for the additional objectives will align with those used in the 2018 trial assessing cardiovascular endpoints among lorcaserin users, insofar as the data support a comparable replication.
		
Variables:	
The key variables are initiation of NB, initiation of lorcaserin (active comparator), time on treatment, and the endpoint of MACE. The individual components of MACE will also be quantified. Covariates will be derived from clinical measurements, past medical history, diagnoses, observations, and prescription records. Multiple imputation will be applied to address missing data, coupled with PS analyses to address confounding.
		
Data Sources:	
EHR and linked claims data from Arcadia Data Research. The data currently cover approximately 75 million people in the U.S.
		
Study Size:	
There are approximately 37,000 apparent NB initiators in the Arcadia data.
 
There are approximately 16,000 apparent lorcaserin initiators.
		
Data Analysis:	
Descriptive statistics of the study cohorts, multiple imputation of missing covariates, estimation of crude incidence rates of MACE among initiators of NB, and adjusted incidence rates of MACE after applying PS matching weights will be calculated (1.0 and 1.1). Analogs to intention-to-treat and per-protocol cohort analyses will be conducted. The analysis will also follow the principles of the RCT DUPLICATE Initiative (2.0 and 2.1) to assess the concordance between findings in an EHR study to those in the lorcaserin cardiovascular safety endpoints trial. In addition, we will conduct a case-crossover study to assess the effects of NB on MACE (2.2) and other sensitivity analyses.
		
Milestones:	
 
 Start of Data Collection End of Data Collection	September 2014 February 2020	
 
	Start of Data Collection End of Data Collection	September 2014 February 2020
Start of Data Collection End of Data Collection	September 2014 February 2020		

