Follow-up time will be calculated separately for each study endpoint. Patients will be followed starting the day after initial exposure until the first of the following censoring events: (1) the study endpoint of interest, (2) death (for those who do not have the endpoint of interest), or (3) end of available data for those who do not have the event of interest (i.e., censoring due to end of available EHR data). Person-time will be calculated by summing the days from cohort entry (day 0) to the date of the first relevant censoring event.

To test the robustness of assumptions about the date of censoring, analyses with differing censoring definitions will be performed, and estimates compared:

- To assess whether the censoring date needs to be adjusted, the physician consultant will review a random sample of patient health profiles to determine whether there is a clear indicator of censoring. Insofar as there appears to be a clear indicator of censoring, the physician will record this date (blinded to exposure), and this information will be used to

adjust the censoring date. Indeed, this information may be treated as an annotation for a machine learning model.

- To account for a patient still being on the insurance plan but not accessing the healthcare system, adjust the end of follow-up to be 6 months, 1 and 2 years following their last healthcare encounter in the EHR.
- To assess the reliability of our method for computing time until censoring in the EHR, compare follow-up times in the EHR to those observed in the claims enrollment files using a subset of those with EHR and claims data.
- To test robustness of the method for computing follow-up time in the EHR, compute the distribution of follow-up times based on enrollment spans within the subset of individuals with claims and EHR data and apply the median follow-up time within populations with particular health profiles.
- To implement a more specific definition of follow-up time, assume that a last healthcare encounter with a primary care provider, endocrinologist, or geriatric care provider in combination with no death information is the end of enrollment.

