### 9.5.2 As-Treated Analysis

The ITT analysis will be juxtaposed with analyses of person-time classified by actual exposure to NB and lorcaserin, grouped into categories of current, recent, and past use. These person-time classifications estimate the effect of being on (or off) the treatment on the rate of the outcomes. Such estimates are often desirable for drug safety questions because they avoid misclassification of exposure that arises in ITT analysis; however, the balance introduced at baseline by PS matching weights may deteriorate as patients switch non-randomly among different study drugs. Therefore, the ITT and *as-treated* analyses are best interpreted together.

To obtain the hazard ratios necessary to compare trial results to those obtained through use of RWD, we will use an ITT analysis for the primary analyses, and as-treated for sensitivity analyses, as was done in the CAMELLIA-TIMI 61 trial.

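### Open-ended ITT follow-up pulls an on-drug MACE excess toward 1, and no planned cohort analysis limits that dilution while keeping the weighted baseline groups

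*Combined protocol and SAP*

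**What the plan says.** Section 6.5.2 starts the clock after cohort entry: "Patients will be followed starting the day after initial exposure until the first of the following censoring events". The censoring events are the endpoint, death and the end of available data. No maximum time from cohort entry is set. That section's sensitivity variants of 6 months, 1 year and 2 years extend follow-up from the last healthcare encounter, so they do not limit time since initiation.

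Section 9.5.1 assigns every day of ITT follow-up to the baseline exposure and acknowledges the consequence: "Classification of person-time in the ITT analysis is subject to exposure misclassification as individuals discontinue treatment". It says that the ITT preserves the weighted balance, and it interprets the result as the effect of starting treatment.

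Section 9.5.2 sets beside it an as-treated analysis by current, recent and past use, without defining those windows. Of these estimates it says: "Such estimates are often desirable for drug safety questions because they avoid misclassification of exposure that arises in ITT analysis". It also concedes that balance may deteriorate there and advises reading the two analyses together. ITT is called primary only for the hazard ratios of the trial comparison; neither analysis is named primary for the NB–lorcaserin MACE comparison.

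On power, section 8.2 reads "Assuming an incidence rate of MACE of 2 per 1,000 years of follow-up within this study" and, with about 37,000 NB initiators, concludes that "it appears that we have greater than 80% power to detect a relative risk of 2.0".

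**The concern.** The study asks whether NB raises MACE risk. If any harm is confined to time on drug, each off-drug year in the ITT adds person-time at the background rate. The estimate falls toward 1 while its interval narrows. A long ITT can therefore give a fairly precise estimate near 1 even when risk on drug is doubled, and that error favours a no-harm reading.

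The planned counterweight in the cohort is the as-treated analysis, whose balance the plan itself doubts. If the ITT is near 1 and current use is raised, the two planned cohort analyses cannot show whether the gap is dilution in one or lost balance in the other.

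The power statement has a related limit. It applies an RR of 2.0 to follow-up as a whole, so it does not describe power for a drug that doubles risk only while it is taken.

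**Working it through.** **Inputs from the documents**
- Background MACE rate: 2 per 1,000 person-years (section 8.2).
- Effect: RR 2.0 (section 8.2).
- NB group: "There are approximately 37,000 apparent NB initiators in the Arcadia data" (section 3).
- Comparator: "There are approximately 16,000 apparent lorcaserin initiators" (section 3).
- Weighting: "Matching weights are the weighting analog of 1:1 PS matching" (section 9.4), so 16,000 per arm is used as the weighted comparison. Both counts are before eligibility criteria.

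**Assumptions, because the documents do not give them**
- Two-sided 5% level.
- Fixed follow-up F.
- Exponential time to stopping.
- Constant background rate, and no lorcaserin effect on MACE.
- No excess risk after stopping, except where carryover is stated.
- No attrition, and no variance inflation from the weights.

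**1. The plan's own power figure.** Take a constant RR of 2.0 and one year of follow-up. Events needed for 80% power are (1.960 + 0.842)² / [p(1−p)(ln 2)²], where p is the NB share.
- 37,000 vs 16,000: 78 events needed; expected 37,000 × 0.004 + 16,000 × 0.002 = 180; power 99%.
- 16,000 vs 16,000: 66 needed; expected 64 + 32 = 96; power 92%.

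The stated inequality holds once mean follow-up exceeds about 0.4 to 0.7 years, provided that RR 2.0 applies throughout. An exact match is not possible: the section 8 text gives no follow-up time, significance level or comparator size, and Figure 3 is not shown.

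**2. Dilution.** With mean time on drug m = median / ln 2, the on-drug share of follow-up is s = m(1 − e^(−F/m)) / F, and IRR = 1 + (2.0 − 1) × s. A 6-month median gives m = 0.5 / 0.693 = 0.721 years. Expected events per arm are E0 = 16,000 × F × 0.002 and E1 = E0 × IRR. The log-scale SE is √(1/E1 + 1/E0), and the interval is centred on the expected IRR.

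| F | s | IRR | E1, E0 | SE | 95% CI | Power |
|---|---|---|---|---|---|---|
| 1 year | 0.541 | 1.541 | 49.3, 32 | 0.227 | 0.99 to 2.40 | 48% |
| 3 years | 0.237 | 1.237 | 118.7, 96 | 0.137 | 0.94 to 1.62 | 34% |
| 5 years | 0.144 | 1.144 | 183.1, 160 | 0.108 | 0.93 to 1.41 | 24% |

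The 3- and 5-year intervals exclude the true on-drug RR of 2.0. The 12-month interval does not.

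A simulation with staggered entry and data ending February 2020 (mean follow-up 2.7 years) agrees: IRR 1.23 and power 30% without a limit, 1.57 and 46% with a 12-month limit.

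**3. When the power ranking changes** (16,000 per arm, on-drug RR 2.0)

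| Median on drug | Carryover | 12 months: IRR, power | 3 years: IRR, power | 5 years: IRR, power |
|---|---|---|---|---|
| 3 months | none | 1.34, 24% | 1.12, about 13% | 1.07, about 10% |
| 6 months | none | 1.54, 48% | 1.24, 34% | 1.14, 24% |
| 12 months | none | 1.72, 69% | 1.42, 75% | 1.28, 65% |
| 24 months | none | 1.85, 80% | 1.62, 96% | 1.48, 97% |
| 6 months | 25% of excess | 1.66, 61.5% | 1.43, 76% | 1.36, 84% |

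The limited ITT is less diluted in every row. It has more power only when the median time on drug is below about 8 months (against 2-year follow-up), 10 months (against 3-year) or 13 months (against 5-year), with no carryover.

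**The case against.** The plan hides nothing. Section 9.5.1 states the misclassification and restricts the ITT to the effect of starting treatment, for which the full-follow-up estimate is valid. Section 9.5.2 pairs it with as-treated results, and nothing lets the ITT alone carry a no-harm conclusion. There is also a case-crossover with a 90-day hazard window, which avoids long off-drug time and confounding by factors that do not vary. A 12-month analysis is thin: with 32 events per arm and a true IRR of 1, SE = √(1/32 + 1/32) = 0.25, and the 95% CI is 0.61 to 1.63.

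All of this stands, and it limits the point to a missing supplementary analysis. It does not fill the gap. The case-crossover is a sensitivity analysis among NB-exposed cases with a different estimand, so it cannot replace a weighted NB–lorcaserin comparison over a defined early period.

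A reader might go further and infer that uncapped ITT loses power in general, or that a 12-month ITT is simply the better analysis. The documents do not support this. They give neither treatment persistence nor any information on risk after stopping, and the last two rows of the second table show the full ITT ahead. Scenarios in which every patient stops exactly at the limit flatter the limited analysis, because it then contains no off-drug time. Nor does the limit restore the stated 80% power when treatment is short.

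**Conclusion.** The concern holds as a gap in the planned set of analyses. If excess risk ends at stopping, the full ITT is diluted progressively with follow-up, and no planned cohort analysis both limits this and keeps patients in their weighted baseline groups. With a 6-month median on drug, a doubling of risk would appear as about 1.24 at 3 years or 1.14 at 5 years, against 1.54 at 12 months.

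These sizes rest on assumed persistence, follow-up and absence of carryover. Attrition and weighting would widen every interval. The direction of dilution does not depend on the persistence chosen, but any power gain from a time limit does. The power claim is arithmetically sound for an RR of 2.0 averaged over follow-up; it does not extend to an on-drug RR of 2.0 followed by off-drug time.

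**What to change.** 1. In section 9.5.1, pre-specify for the main objective a supplementary ITT truncated at 12 months after cohort entry, with the same matching weights and weighted Poisson model. Versions at 6 and 24 months are optional; they would show how far the result depends on a horizon that the documents cannot derive from persistence data.
2. Report it beside the full-follow-up ITT and as-treated results, not instead of them.
3. State that the full ITT estimates the effect of starting treatment and must not be read alone as excluding an on-drug effect.
4. In section 8.2, state that the power for RR 2.0 refers to the RR averaged over follow-up and makes no allowance for time off drug.

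The cost is one further run of the same model per horizon and a few sentences of text. The downside is fewer events (about 32 in the comparator group at 12 months with 16,000 patients) and so a wider interval.

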### 9.5.2 As-Treated Analysis

The ITT analysis will be juxtaposed with analyses of person-time classified by actual exposure to NB and lorcaserin, grouped into categories of current, recent, and past use. These person-time classifications estimate the effect of being on (or off) the treatment on the rate of the outcomes. Such estimates are often desirable for drug safety questions because they avoid misclassification of exposure that arises in ITT analysis; however, the balance introduced at baseline by PS matching weights may deteriorate as patients switch non-randomly among different study drugs. Therefore, the ITT and *as-treated* analyses are best interpreted together.

To obtain the hazard ratios necessary to compare trial results to those obtained through use of RWD, we will use an ITT analysis for the primary analyses, and as-treated for sensitivity analyses, as was done in the CAMELLIA-TIMI 61 trial.

### 9.5.3 Statistical Model for Cohort Analysis

For all primary study objectives, weighted Poisson models will be used to estimate IRDs and IRRs (and 95% CIs), adjusted for all covariates included in the PS model. Robust variance estimators will be used to account for the weighting. Analyses will be conducted amongst the overall NB cohort and also stratified by initiators of CONTRAVE® and those with overlapping, concomitant use of Naltrexone and Bupropion.

For the secondary objective of assessing the comparability of findings in a RWD cohort with the lorcaserin clinical trial, we will conduct a time-to event analysis in the propensity-score matched cohort. We will produce hazard ratios (HR) and 95% confidence intervals using a weighted Cox proportional-hazards model with the stratification factor as a covariate.

Additionally, informed by previous work in the RCT DUPLICATE Initiative, we will examine the following metrics in concert to assess the comparability in findings between the CAMELLIA-TIMI 61 trial and findings in the data:

- Regulatory agreement, which is the ability of the study using RWD to replicate the direction and magnitude of the RCT;

- Estimate agreement, defined as a HR from the replication study that was within the 95% CI for the RCT estimate;
- Standardized difference between the RCT and replication effect estimate, with a p-value < 0.05 considered statistically significant.

Conditional logistic regression models will be used to compare the odds of exposure to NB in the hazard window to the odds of exposure in the referent window (i.e., odds ratio) for the case cross-over design.

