## 6 RESEARCH METHODS

### 6.1 Study Design

A retrospective cohort study design will be used for the main objective and endpoints. Initiators of NB will be identified between September 2014 and February 2020. Contemporaneously, we will identify all lorcaserin users between 2012 and 2020. A self-controlled, case-crossover design will be used for the sensitivity analysis (2.2).

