### 6.5.3 Covariates

A range of demographics will be assessed for each patient at cohort entry, including the following:

- Age;
- Sex;
- Race/ethnicity.

A set of comorbidities will be assessed in the 180 days before cohort entry, including the following:

- Acute myocardial infarction;
- Stroke;
- Dyslipidemia;
- Type 2 diabetes mellitus;
- Transient ischemic attack;
- Hypertension;
- Heart failure;
- Unstable angina;
- Peripheral vascular disease;
- Coronary heart disease;
- Cerebrovascular disease;
- Chronic kidney disease;

- Sleep apnea;
- Mood disorders.

A set of concomitant medications will be assessed in the 180 days before cohort entry, including the following:

- Medications that affect cardiovascular outcomes, including:
  - Antihypertensives;
  - Statins;
  - Anticoagulants;
  - Antiplatelets;
  - Antihyperglycemics.
- Other medications listed in the CONTRAVERE® Prescribing Information Drug Interactions, including:
  - Selective serotonin reuptake inhibitors;
  - Tricyclic antidepressants;
  - Antipsychotics;
  - Beta-blockers;
  - Type 1C antiarrhythmics (e.g., propafenone and flecainide);
  - Digoxin;
  - Antiplatelets.

A set of relevant laboratory test results and biometric values will be assessed during the 180 days before cohort entry, including the following:

- BMI;
- Blood glucose or HbA1c;
- Liver function;
- Dyslipidemias;
- Resting heart rate;
- Respiratory rate;
- Systolic blood pressure;
- Diastolic blood pressure;
- Glomerular filtration rate/serum creatinine.

Where multiple values are available, the most recent will be selected. Where no value is present, multiple imputation procedures will be used to generate a value under the assumption that the values are missing at random.

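### The main Poisson model has no term for time since entry or attained age, so the ITT rate ratio, and more surely the on-versus-off as-treated contrast, can mix drug effect with elapsed time in a direction the documents do not settle

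*Combined protocol and SAP*

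**What the plan says.** - **Main model (section 9.5.3).** For the primary objectives, "weighted Poisson models will be used to estimate IRDs and IRRs (and 95% CIs), adjusted for all covariates included in the PS model". The weighted Cox model in the same section serves only the comparison with the lorcaserin trial.
- **Rates (section 9.3).** "The incidence rate for each group is the cumulative number of observed endpoint events, divided by the total person-years of follow-up". This gives one average rate per group.
- **Covariates (section 6.5.3).** "A range of demographics will be assessed for each patient at cohort entry", age among them. The other covariates come from the 180 days before entry. Nothing is updated during follow-up.
- **Entry (section 6.1).** "Initiators of NB will be identified between September 2014 and February 2020". For the comparator: "Contemporaneously, we will identify all lorcaserin users between 2012 and 2020".
- **End of follow-up (section 6.5.2).** Follow-up stops at the endpoint, at death, or at "end of available data for those who do not have the event of interest". There is no common maximum. The listed sensitivity analyses vary the censoring date; none models how the rate changes over time.
- **As-treated analysis (section 9.5.2).** Person-time is classed as current, recent or past use. "These person-time classifications estimate the effect of being on (or off) the treatment on the rate of the outcomes".
- **Propensity score (section 9.4).** Calendar time of initiation is named as a covariate, but in the paragraph about the trial-comparability cohort. The list in section 6.5.3 does not contain it.

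**The concern.** A Poisson model with baseline covariates only compares the average rate in one group's follow-up with the average rate in the other's. That is harmless if the rate is constant, or if both groups have the same distribution of time since entry. Neither is assured here.

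Two contrasts are exposed:

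- **ITT, NB versus lorcaserin.** If lorcaserin patients enter earlier and are followed longer, more of their person-time lies late after entry and at older attained age. Adjusting for age at entry does not correct this.
- **As-treated, current versus past use.** In a new-user cohort, current use comes soon after entry and past use later. This holds within one drug, needs no difference in entry dates, and cannot be removed by baseline weights. Section 9.5.2 warns that balance may deteriorate through switching, but does not mention elapsed time.

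The study is a cardiovascular safety study whose report goes to FDA (section 13). An estimate near 1 would be read as reassurance, so an avoidable shift of several percent matters most there.

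**Working it through.** **Scale.** The plan gives no figure for this point. Its own figure, more than 80% power for a relative risk of 2.0 (section 8.2), sets the scale. Inputs: about 37,000 NB and 16,000 lorcaserin initiators (section 3), 2 MACE per 1,000 person-years, and mean follow-up of f years. With two-sided 0.05 assumed, power = Φ( ln 2 / √[1/(37,000 × 0.004 f) + 1/(16,000 × 0.002 f)] − 1.96 ).

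- f = 0.5: 74 and 16 events, power 71%.
- f = 0.75: 111 and 24 events, power 87%.

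The 80% mark is passed at f = 0.62 years. The claim is plausible but cannot be reproduced exactly, because the text gives no follow-up and Figure 3 is not shown. At the null with f = 2, the standard error of log IRR is √(1/148 + 1/64) = 0.150, a 95% confidence factor of about 1.34.

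**ITT contrast with no drug effect.** Assumptions, because the documents give neither follow-up by group nor a hazard shape:

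- hazard 0.002 × exp(g × years since entry) in both groups;
- uniform entry from 2014.7 (NB) or 2012.5 (lorcaserin) to 2020.15;
- data ending in February 2020 or November 2022;
- loss of 0, 0.2 or 0.5 per year.

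With no loss and a February 2020 end, follow-up is uniform on 0 to T, where T = 5.45 years (NB) or 7.65 years (lorcaserin). The mean is T/2, or 2.73 and 3.83 years. The average rate relative to the rate at entry is A = 2(e^{gT} − 1 − gT)/(gT)².

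| g per year | A, NB | A, lorcaserin | Null IRR |
|---|---|---|---|
| +5% | 1.0974 | 1.1407 | 0.962 |
| +8% | 1.1627 | 1.2395 | 0.938 |
| +10% | 1.2094 | 1.3123 | 0.922 |
| −10% | 0.8406 | 0.7872 | 1.068 |

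At +10% the spurious IRD is 2 × (1.2094 − 1.3123) = −0.21 per 1,000 person-years.

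Over the other loss rates and data ends (1,000,000 simulated follow-up times per group):

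| Data end | Loss per year | Null IRR, +5% to +10% | Null IRR, −10% |
|---|---|---|---|
| Feb 2020 | 0 | 0.962 to 0.922 | 1.068 |
| Feb 2020 | 0.2 | 0.976 to 0.949 | 1.042 |
| Feb 2020 | 0.5 | 0.989 to 0.976 | 1.019 |
| Nov 2022 | 0 | 0.963 to 0.922 | 1.061 |
| Nov 2022 | 0.2 | 0.981 to 0.959 | 1.029 |
| Nov 2022 | 0.5 | 0.995 to 0.988 | 1.008 |

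If lorcaserin uptake is assumed to be early rather than uniform, the range at +5% to +10% widens to 0.86-0.985. With the same entry window, uptake and loss in both groups, the unbanded IRR is 1.000 (checked at +10%).

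**As-treated contrast with no drug effect.** Further assumptions: exponential duration of use U with mean 3 to 12 months, and a 90-day recent-use gap. With follow-up F and H(x) = (e^{gx} − 1)/g:

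- current rate ∝ Σ H(min(F, U)) / Σ min(F, U);
- past rate ∝ Σ [H(F) − H(min(F, U + 90 d))] / Σ [F − min(F, U + 90 d)].

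| Contrast | Setting | Null ratio |
|---|---|---|
| Current v past NB | +5% to +10%, Feb 2020, no loss | 0.82-0.92 |
| Current v past NB | +5% to +10%, Nov 2022, no loss | 0.73-0.88 |
| Current v past NB | +5% to +10%, loss 0.5, both ends | 0.83-0.94 |
| Current v past NB | −10%, all settings | 1.13-1.32 |
| Current NB v current lorcaserin | +5% to +10%, no loss | 0.99-1.00 |

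**Effect of banding.** Splitting follow-up into 3-month bands of time since entry and taking a Mantel-Haenszel ratio returns the ITT null to 0.9998-1.0002 for g = −20%, +5%, +8% and +15%, at every loss rate and both data ends.

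**The case against.** Most of the opposing case limits the ITT part.

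- **Direction.** A reader might infer that the model makes NB look safer. That needs two facts the documents do not give: longer weighted follow-up for lorcaserin, and a MACE rate that rises after initiation. A falling rate (early events, depletion of susceptible patients) reverses the sign. This objection stands.
- **Loss to follow-up.** An IRR of 0.92-0.96 is the no-loss end of the range. Section 6.5.2 ends follow-up with each patient's available data, and loss of 0.2-0.5 per year brings the IRR to about 0.95-0.99. This stands too.
- **Calendar time.** If initiation date is in the main propensity score, a lorcaserin starter before September 2014 has a score near 0 and a matching weight PS/(1 − PS) near 0. The entry-window gap then largely vanishes. This stands if the covariate applies, but the placement in section 9.4 and the silence of section 6.5.3 leave that open. The abstract's milestones (September 2014 to February 2020) might also suggest a shared window, but sections 6.1 and 6.5.1 give lorcaserin a longer one.
- **As-treated figures.** Section 9.5 describes both analyses as NB relative to comparators, and current NB versus current lorcaserin is almost unaffected. The large figures therefore do not apply to that contrast. They do apply to the on-or-off reading that section 9.5.2 itself offers, and calendar time in the propensity score does not repair it.
- **Precision.** A shift of 1-8% is small beside a relative risk of 2.0 and a confidence factor near 1.34. True, but widening the interval does not remove a bias, and the remedy is cheap.
- **Cox model.** Section 9.5.2 explains that hazard ratios are needed to match the trial. Using another regression there is not a defect.

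Figure 1 is not shown, so its follow-up layout could not be checked.

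**Conclusion.** The concern holds in conditional form. The main model as written has no time-since-entry or attained-age term, the stated entry windows differ by about two years, and follow-up has no common maximum. If risk is not constant and weighted follow-up differs, the ITT IRR is biased: towards no harm if risk rises and lorcaserin follow-up is longer, and the other way if risk falls with that same follow-up pattern. Under uniform entry the null ITT IRR is about 0.92-0.99 at +5% to +10% per year and 1.01-1.07 at −10%. The entry-window part largely goes away if calendar time is in the main propensity score.

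The firmer problem is reading current and past use as the effect of being on or off treatment. The null ratio for NB is about 0.73-0.94 at +5% to +10% per year and 1.13-1.32 at −10%. Growth rates, loss rates, uptake and duration of use are all assumptions. The documents do not show that the plan favours NB. The change should be made before analysis, but the point does not invalidate the design.

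**What to change.** In section 9.5.3:

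1. Split each patient's person-time by time since cohort entry (for example 0-3, 3-12, 12-24 and over 24 months) and by attained age. Include the bands in the weighted Poisson model for both the ITT and the as-treated analyses. Alternatively, also apply the weighted Cox model, on time since entry, to NB versus lorcaserin.
2. Compute the IRD from weighted rates standardised to a common distribution of time since entry.
3. State in sections 6.5.3 and 9.4 that calendar time of initiation is in the main propensity score.
4. Report weighted follow-up by group.
5. In section 9.5.2, tie the on-or-off interpretation to the time-banded estimates.

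The cost is SAP wording, a person-time split in the program and a negligible loss of precision. No new data are needed.
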